IDE	Investigational Device Exemption
IRB	Institutional Review Board
iRIS	Electronic IRB software system
MOP	Manual of Procedures
N	Number (typically refers to participants)
NIDCR	National Institute of Dental and Craniofacial Research, NIH, Department of Health and Human Services
NIH	National Institutes of Health
OHRP	Office for Human Research Protections
PHI	Protected Health Information
PI	Principal Investigator
PO	Program Official, NIDCR, NIH
PRMC	Protocol Review and Monitoring Committee
PRMS	Protocol Review and Monitoring System
SAE	Serious Adverse Event/Serious Adverse Experience
SOC	Standard of Care

SOC	Safety Oversight Committee
SOP	Standard Operating Procedure
SC	Study Coordinator
US	United States

PROTOCOL SUMMARY

Title:	Partnership to Establish a Practice Based Network to Assess for Head and Neck Cancers Using a Low-Cost Portable Flexible Nasopharyngoscope – Optimization Phase
Précis:	
The optimization phase of this study will be conducted at Duke University. The implementation phase will be done in Vietnam and conducted under a separate protocol. During optimization, direct comparison between the standard flexible nasopharyngoscope scope used in the US. with the new mobile flexible nasopharyngoscope (FNS) will be done to optimize the FNS design to be noninferior to the standard of care (SOC) exam. Any patient who meets clinical indication for a nasopharyngoscope exam is eligible for the study. If consent is given the subject will first undergo the “SOC” scope endoscopy. Then the FNS exam will be performed using the mobile device. A post-procedure survey will then be administered and completed by both the provider and subject. Post-procedure data will be collected in three areas: technical assessment (i.e. image, lighting, and steering), physician feedback (i.e. ease of use, image quality), and subject feedback (i.e. perceived pain). Data collected during optimization will inform of final adjustments needed to the mobile FNS device before it is used to conduct the implementation phase in Vietnam. A protocol amendment will be submitted to include details about the implementation phase in Vietnam before study activities begin there.

Objectives:	
Optimize the low cost FNS by comparing to SOC scopes at Duke University Medical Center
 
We will compare the use and reliability of the FNS scope to SOC scopes available at Duke University Medical Center. This will include image quality to see structures, lighting, and steering mechanism. Key objectives include ease of use, image quality, and perceived pain. The technical and subjective feedback will optimize the device to gain efficiencies and improve tolerability. Success is considered to be that the FNS is overall non-inferior to the current SOC scopes.
 
The expected outcome is to have an optimized FNS scope for production and widespread implementation and use

Population:	Up to 50 subjects 18 years or older who meet clinical criteria to undergo a SOC endoscopic exam
Phase or Stage:	N/A
Number of Sites:	1 site
Description of Intervention:	The FNS is used for assessment of the entire upper aerodigestive tract by Ear, Nose, and Throat (ENT) doctors or otolaryngologists and is part of SOC in the USA. This scope is inserted through the nasal passages into the pharynx, enabling a full view of all areas at risk for Head and Neck Cancer (HNC). Study participation ends once the post intervention survey is completed.
Study Duration:	3 months
Subject Participation Duration:	About 30 minutes
Estimated Time to Complete Enrollment:	2 months

Recruitment: Adult subjects that will undergo SOC endoscopy at the Head and Neck Surgery and Communication Sciences clinic at Duke will be approached by their treating physician if they would be interested in participating in this study. If they are interested, the study team will approach them to review the written consent form. Once signed, the SOC procedure will take place followed by the study scope procedure. The physician will complete their portion of the post procedure survey and assess for adverse effects. The subject will complete a single question on the survey focused on comparing the pain from both procedures.

2 INTRODUCTION: BACKGROUND INFORMATION AND SCIENTIFIC RATIONALE

2.1 Background Information

Head and neck cancers (HNC) are the 6th most common cancers worldwide, with an incidence of 550,000 patients/year and a mortality rate of 356,000 patients/year (International; Jemal et al., 2011). Most HNC occur in the upper aerodigestive tract, which includes nasopharyngeal, tonsil, tongue, hypopharyngeal and larynx (voicebox) cancers (**Figure 1**).

Proper examination of the head and neck region without specialized equipment and devices makes HNC difficult to diagnose at earlier stages.

A critical tool that has improved the examination of the areas where HNC can present is the FNS. The FNS is used for assessment of the entire upper aerodigestive tract by Ear, Nose, and Throat (ENT) doctors or otolaryngologists and is part of SOC in developed countries. This scope is inserted through the nasal passages into the pharynx, enabling a full view of all areas at risk for HNC. Furthermore, it allows for assessment of function of this area (e.g. vocal cord movement) that can provide important information for early detection of cancers. Currently, FNS systems at tertiary medical centers in the US cost around \$10,000 and are large and heavy, limiting their use to a single room. **Figure 2** shows an example of a currently available system that includes a monitor, scope, light source, image processor, and printer.

[figure not shown]

Figure 1: Upper aerodigestive tract

Figure 2: FNS System

This study seeks to develop a low cost FNS scope that can be used in low resource settings. The hope is that with an affordable device, this will improve the ability to screen for HNC. The optimization phase will compare this new prototype with standard SOC scopes used at Duke University.

2.2 Rationale

There is a rising global incidence of HNC in LMICs. Specifically, Vietnam has one of the highest incidences of HNC and the healthcare system is not meeting this need. Local provincial/district hospitals often lack scopes that provide adequate evaluations for patients. National/central hospitals have proper equipment for examinations, but are

overburdened by patients, many of which could have been cared for and treated locally if they could have been examined properly at local hospitals. A low cost FNS would significantly improve the ability of ENT doctors at these local hospitals to properly examine patients. Furthermore, training and equipping users at the district/provincial hospitals with this scope could improve clinical decisions as to which patients can be locally treated vs. referred. This could result in refocusing patient care burden at national specialty hospitals to conditions that truly need tertiary care (i.e. advanced HNC), rather than conditions that could be addressed at provincial/district hospitals.

Based on preliminary work, we have collected feedback from physicians on how to improve on our basic prototype. This includes providing consistent image quality to visualize the structures in the upper aerodigestive tract as well as improve lighting. Furthermore, the diameter of the scope is to be decreased to improve scope insertion and patient comfort. These factors are being incorporated into the first prototype to be used in this current clinical study. The goal is to optimize the low-cost scope as compared to the current SOC scope used at Duke.

2.3 Potential Risks and Benefits

2.3.1 *Potential Risks*

The SOC scope exam is done through the nasal cavity. Risks for the SOC include stiff neck, sore throat, temporary perceived difficulty breathing, bleeding, and minor damage to the lining of the airway. These are all considered very rare and self- limiting.

The risks to the subjects using the FNS include stiff neck, sore throat, temporary perceived difficulty breathing, bleeding, and minor damage to the lining of the airway. These are all considered very rare and self- limiting.

2.3.2 *Potential Benefits*

There are potential benefits to large parts of the developing world, if an affordable, easily portable scope proves clinically acceptable. There may be benefit for earlier detection of cancer or other lesions using the FNS in settings in which no scope device is available.

3 OBJECTIVES AND OUTCOME MEASURES

OBJECTIVES:

We will collect user feedback and reliability of the low-cost FNS scope as compared with the currently used SOC scope procedure. Collection of technical issues with the low cost FNS prototypes will also include steering, lighting, video, fogging, image capture.

Key objectives include comparisons between the SOC scope and FNS:

Primary

Ease of use

Compared with the first scope, how easy was the second scope to use?

Very Hard	Harder	same	Easier	Very Easy
1	2	3	4	5

Secondary

1) Image Quality

Rate the video quality of the first scope: (Poor) 1 2 3 4 5 (Excellent)

Rate the video quality of the second scope: (Poor) 1 2 3 4 5 (Excellent)

2) Perceived pain by subjects

Did you experience more, the same, or less pain/discomfort with the second scope compared with the first scope?

much more about the same much less

1	2	3
---	---	---

OUTCOME MEASURES

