3.2 Secondary

Objective	Brief Description/Justification of Outcome Measure	Outcome Measured By	Time Frame
Assess image quality and subject pain	Comparison of image quality between the SOC scope and FNS as well as subject perception of pain between the two exams will help to inform modifications needed for prototype optimization.	image quality of each scope: rated 1(poor) to 5 (excellent) perceived pain by subjects between scopes: Much More 1 About the same 2 Much Less 3	up to 2 months

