12.3 Final Analysis Plan

Statistical Analysis – Aim 1: Optimization Phase.

1. Outcome 1 (Primary): The primary outcome is ease of use comparison between the FNS to the SOC scope (score of 1 – 5, with 1 being very hard and 5 being very easy).
2. Outcome 2 (Secondary): Quality of the image (image quality score range 1-5, with 1 being poor and 5 being excellent).
3. Outcome 3 (Secondary): Perceived pain between the FNS to the SOC scope (pain score range of 1 – 3, with 1 being much more and 3 being much less).

Scenario 1:

Success of this first phase 1 (Aim 1) after evaluating 37 subjects is defined as - (1) at least 90% response of ease of use of second scope compared to first score to range from same to excellent (3 to 5); and (2) 90% responding to better video quality of second scope compared to first (score ranging from same to excellent (3 to 5); and (3) 90% responding to pain score of same or much less (2 or 3); In short, this phase is a success if 90% respond to same to excellent/much less on all 3 of the outcomes.

[figure not shown]
Scenario 2: If the rate is between 50 to < 90% for any three outcomes in a sample from 37, then the plan is to proceed recruiting more subjects until 50 are recruited. At 50 subjects, if in scenario 1 then phase 1 is a success and phase 1 is complete; if not, fine tune the prototype.

Scenario 3: If the rate is < 50% for any one of the 3 outcomes described above, then the plan is to proceed to fine tuning the prototype.

The primary outcome of ease of use of scope as reported by the physicians, will be examined between the two different scopes, at the simplest level, using paired Z-test if the scores (or transformed scores) are normally distributed or by using Wilcoxon test if the scores are non-normal.

The analysis for secondary outcomes of the change in the quality of the videos and pain will each be examined using paired Z-test, if the change (or transformed scores) is normally distributed or by Wilcoxon test if the change is non-normal. Assumptions of each of these tests will be examined. The significance of each of the outcomes will be examined at alpha = 0.05. The reliability of this instrument (using intra-class-correlation (ICC)) will be first assessed by using the data from the first 50 subjects. If ICC is < 0.9, we will include training component and necessary adjustment for the physicians.

See diagram below

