Piker, E. G., Schulz, K., Parham, K., Vambutas, A., Witsell, D., Tucci, D., Lee, W. T. (2016). Variation in the Use of Vestibular Diagnostic Testing for Patients Presenting to Otolaryngology Clinics with Dizziness. *Otolaryngol Head Neck Surg*, 155(1), 42-47. doi:10.1177/0194599816650173

Powell, B. J., McMillen, J. C., Proctor, E. K., Carpenter, C. R., Griffey, R. T., Bunger, A. C., Glass, J. E., York, J. L. (2012). A compilation of strategies for implementing clinical innovations in health and mental health. *Med Care Res Rev*, 69(2), 123-57. doi: 10.1177/1077558711430690.

Powell, B. J., Waltz, T. J., Chinman, M. J., Damschroder, L. J., Smith J. L., Matthieu M. M., Proctor, E. K., Kirchner, J. E. (2015). A refined compilation of implementation strategies: results from the Expert Recommendations for Implementing Change (ERIC) project. *Implement Sci*, 12, 10:21. doi: 10.1186/s13012-015-0209-1.

Schroy, P. C., 3rd, Wilson, S., & Afdhal, N. (1996). Feasibility of high-volume screening sigmoidoscopy using a flexible fiberoptic endoscope and a disposable sheath system. *Am J Gastroenterol*, 91(7), 1331-1337.

Vo, Q. T., Pham, D., Choi, K. J., Nguyen, U. T., Le, L., Shanewise, T., Lee, W. T. (2017). Solar-powered hearing aids for children with impaired hearing in Vietnam: a pilot study. *Paediatr Int Child Health*, 1-6. doi:10.1080/20469047.2016.1276119

SUPPLEMENTAL MATERIALS

Post-Procedural Survey By Clinician who performed the scope exam

(Provider questions once the SOC and study FNS exams are completed):

TECHNICAL ASSESSMENT OF FNS

Were you able to complete the first scope procedure to your satisfaction?

1=no 2=somewhat 3=yes

Were you able to complete the second scope procedure to your satisfaction

1=no 2=somewhat 3=yes

Were you able to view all the structures of concern using first scope ? Y/N

If no, please explain:

Were you able to view all the structures of concern using second scope ? Y/N

If no, please explain:

Did the patient appear to have more, the same, or less discomfort with the second scope?

much more about the same much less
1 2 3

If much more: please describe why:

Were there technical issues with the second prototype scope? Y/N (if Yes, please explain below)

- _____ steering
 - _____ lighting
 - _____ video
 - _____ fogging
 - _____ image capture
 - _____ other

Ease of use: Aim 1:

Compared with the first scope, how easy was the second scope to use?

Very hard Harder same Easier Very easy

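### The pain item has no answer for moderately more pain, and the gap lies on the success cut, where it can only favour the FNS

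*Combined protocol and SAP*

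**What the plan says.** The stem of the subject item in Section 3 names three directions: "Did you experience more, the same, or less pain/discomfort with the second scope compared with the first scope". The answers printed beneath it are "much more about the same much less", coded 1 to 3. The outcome table in Section 3.2 ties each label to its code ("Much More 1 About the same 2 Much Less 3"), and Section 12.3 repeats the range ("with 1 being much more and 3 being much less"). The subject form in the Supplemental Materials has the same three options. The clinician form has a parallel item, "Did the patient appear to have more, the same, or less discomfort with the second scope", with the same options, and asks for an explanation only when *much more* is ticked.

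Scenario 1 in Section 12.3 sets the pain criterion as "90% responding to pain score of same or much less (2 or 3", so only code 1 is a failure. Pain carries full weight in the decision: "this phase is a success if 90% respond to same to excellent/much less on all 3 of the outcomes". The Protocol Summary says of the subject's part: "The subject will complete a single question on the survey focused on comparing the pain from both procedures".

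**The concern.** The stem and the answers do not match. A subject for whom the FNS hurt somewhat more, but not much more, must choose between overstating the difference (code 1, failure) and denying it (code 2, success). The missing category is the one that separates pass from fail.

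Somewhat less pain has no matching answer either, but under Scenario 1 it counts as success whichever neighbouring option is ticked. A somewhat-more subject who rounds up to *much more* is a failure, as would be the case with a matching option. One who rounds down becomes a success. Measured against a scale on which any clear worsening fails, the pass rule can therefore err in one direction only.

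At stake is a go/no-go decision. Section 4 sets the goal that the FNS should match or better the SOC scope on the outcome measures, after which no further prototype is needed. Section 12.1 names perceived pain in the non-inferiority hypothesis. A prototype that hurts moderately more in a sizeable minority could meet the pain criterion, and the recorded data could not show that this had happened. The paired test in Section 12.3 uses the same 1 to 3 score and cannot recover the lost category.

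**Working it through.** **The plan's own figure.** Section 12.2 states that n = 37 gives a two-sided 95% interval of 0.76 to 0.96, width 0.2, at a sample proportion of 0.9. The Wilson score interval reproduces it. With z² = 3.8416 and z²/37 = 0.1038:
- centre = (0.9 + 0.0519)/1.1038 = 0.862
- half-width = 1.96 × √(0.09/37 + 3.8416/(4 × 37²))/1.1038 = 0.0994
- limits 0.763 and 0.962, width 0.199

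This confirms the arithmetic for 37. It says nothing about how pain is measured.

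**The two scales side by side** (Sections 3, 3.1, 3.2 and 12.3).

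| Outcome | Adverse codes | Neutral code | Success codes |
|---|---|---|---|
| Ease of use | very hard (1), harder (2) | same (3) | 3 to 5 |
| Pain | much more (1) | about the same (2) | 2 to 3 |

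The ease-of-use scale has an intermediate adverse category, and it counts as failure. The pain scale has none.

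**Pass rule for pain taken alone** (Section 12.3, Scenarios 1 and 2, applied per outcome).
- 90% of 37 is 33.3, so at least 34/37 passes.
- 50% of 37 is 18.5, so 19 to 33 of 37 continues to 50.
- 90% of 50 is 45, so at least 45/50 then passes.

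For a recorded success rate p:

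P(pass) = P(X₃₇ ≥ 34) + Σ (k = 19 to 33) P(X₃₇ = k) × P(X₁₃ ≥ 45 − k)

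where X₃₇ and X₁₃ are binomial with probability p.

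**Recorded rate.** Let a be the share with much more pain, b the share with somewhat more, and d the fraction of b who tick *about the same*. The recorded rate is p = 1 − a − b(1 − d). The documents give none of these three, so all are assumptions.

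With a = 0.05, b = 0.20 and 0.75 the same or less:

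| d | p | Pass at 37 | Pass at 50 after continuing | Total |
|---|---|---|---|---|
| 1 (all) | 0.95 | 0.888 | 0.079 | 0.967 |
| 0.5 (half) | 0.85 | 0.174 | 0.085 | 0.258 |
| 0 (none) | 0.75 | 0.009 | 0.004 | 0.012 |

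With a = 0.05 and b = 0.05, the total is 0.967 for d = 1 (p = 0.95) and 0.651 for d = 0 (p = 0.90).

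The row d = 0 is also what a scale with a matching *more* option would give. At d = 0.5 the pass probability is 0.258/0.012, about 20 times that value.

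**The case against.** **The diverted share is unknown.** Only one option points towards more pain, and the stem asks about more pain, so some somewhat-more subjects may tick *much more*. A reader might infer that the item is blind to moderate worsening, or that everyone with it is pushed into a success. Nothing in the documents supports full diversion. This objection stands, and it is why the result is given for all, half and none.

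**Pain is not judged alone.** Success needs all three outcomes. Pain could meet 90% at 37 and be judged again at 50 because another outcome fell short. At 50 subjects alone (at least 45/50), the three cases above give 0.96, 0.22 and 0.007, so the pattern holds. Section 12.2 also words success differently, as a proportion between 0.76 and 0.96 at 37, that is 29 to 35 subjects. On that reading, rates of 0.95 and 0.75 pass with probability 0.56 and 0.40. The figures here therefore depend on taking Section 12.3 as the rule.

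**Some tolerance may be intended.** Non-inferiority normally allows a margin, and *about the same* could serve as one. But no pain margin is stated, and the ease-of-use scale fails its intermediate adverse category. At best the tolerance is undefined.

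**Other signals exist.** The clinician form records completion, technical problems and adverse events, and Section 5.4.2 records reasons for stopping the FNS exam. None of these is a graded pain measure. A reader might also infer that the item hides the evidence needed to reduce the scope's diameter. Section 2.2 does not support that: the smaller diameter came from preliminary feedback and is already going into the first prototype.

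**Conclusion.** The concern holds as a measurement fault in a secondary outcome that gates success. The mismatch between stem and options is certain, and it recurs wherever the options are printed. For the Scenario 1 rule its direction is also certain: it can only help the FNS. That does not carry over to the paired test, where the missing *somewhat less* could work the other way.

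The size is not known. Under the assumed split of 5%, 20% and 75%, the chance of meeting the pain criterion lies anywhere from 0.01 to 0.97 depending on how subjects round, with 0.26 if half round down. If few subjects have moderately more pain, or most of them tick *much more*, the effect on the decision is small. The documents do not show that an inferior prototype will pass. They show that the recorded data could not tell whether one had.

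**What to change.** Use five comparative levels in the subject item: much more (1), somewhat more (2), about the same (3), somewhat less (4), much less (5). Count 3 to 5 as success. Make the same change to the clinician's discomfort item, and prompt for an explanation at *somewhat more* as well as *much more*. Update the wording and codes together in Sections 3, 3.2 and 12.3 and in both survey forms.

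Five levels are better than relabelling the three options as more, about the same and less. The bare relabel would make any perceived increase, however slight, indistinguishable from a marked one. The FNS is always the second insertion, about a minute after the SOC scope (Sections 4 and 7.1), so part of any increase may come from repeat passage and not from the device. Separating degrees keeps that visible.

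The cost is a REDCap edit and an amendment, which under Section 15.2 needs IRB and NIDCR approval. The sample size of 37, extendable to 50, is unaffected. The downside is a pain success rate that may be less favourable, partly because of the fixed order.

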3.1 Primary

Objective	Brief Description/Justification of Outcome Measure	Outcome Measured By	Time Frame
Assess ease of use by end users between the SOC scope and FNS	We are comparing the ease of use between the FNS to the SOC scope. This will impact the design considerations and modification for the prototype optimization.	Compared with the first scope, how easy was the second scope to use? Very Hard 1 Harder 2 Same 3 Easier 4 Very Easy 5	Up to 2 months

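### The primary ease-of-use item pairs a comparative question and comparative middle options with absolute end labels, so an answer read literally can land on the wrong side of the success cut

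*Combined protocol and SAP*

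**What the plan says.** Section 3 puts one question to the clinician after both exams: "Compared with the first scope, how easy was the second scope to use". Section 3.1 gives the purpose as a comparison, "We are comparing the ease of use between the FNS to the SOC scope", and lists the answers as "Very Hard 1 Harder 2 Same 3 Easier 4 Very Easy 5". The clinician survey in the Supplemental Materials carries the same five labels: "Very hard Harder same Easier Very easy".

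Section 12.3 calls the primary outcome an ease-of-use comparison of the FNS with the SOC scope, then describes the score "with 1 being very hard and 5 being very easy". Scenario 1 requires "at least 90% response of ease of use of second scope compared to first score to range from same to excellent (3 to 5"), and sums up: "this phase is a success if 90% respond to same to excellent/much less on all 3 of the outcomes".

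The subject pain item in section 3.2 is also a comparison of the two scopes, but its ends are comparative: "Much More 1 About the same 2 Much Less 3".

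**The concern.** The stem and options 2, 3 and 4 place the FNS relative to the SOC scope. Options 1 and 5 describe how hard or easy a scope is in its own right. No section tells the rater to take the ends as relative, and section 12.3 repeats them, adding *excellent* for the top of the range.

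The two absolute labels lie on opposite sides of the success cut, so a literal answer can turn an unfavourable comparison into a success or a neutral one into a failure. The comparison cannot be rebuilt from other items, because the survey collects no separate ease rating for each scope, as it does for video quality. The paired Z-test or Wilcoxon test in section 12.3 also has only this one score to work on, so it is meaningful only if the score is a true comparison centred on 3.

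**Working it through.** **1. The labels against the cut.**

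| Code | Label | Literal frame | Counts toward the 90%? |
|---|---|---|---|
| 1 | Very Hard | absolute | no |
| 2 | Harder | relative to SOC | no |
| 3 | Same | relative to SOC | yes |
| 4 | Easier | relative to SOC | yes |
| 5 | Very Easy | absolute | yes |

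Two kinds of exam cross the cut on a literal reading:

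- (a) Difficult anatomy, both scopes very hard: the relative answer is 3 (success), the literal answer is 1 (failure).
- (b) Easy anatomy, FNS very easy but less so than SOC: the relative answer is 2 (failure), the literal answer is 5 (success).

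A literal answer on the same side of the cut (for example 5 where 4 was meant) does not affect the rule.

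**2. The plan's own figure.** Section 12.2 gives n = 37 for a 95% interval of width 0.2 at a proportion of 0.9, with limits 0.76 and 0.96. The Wilson interval reproduces this:

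- centre = (0.9 + 1.96²/74) / (1 + 1.96²/37) = 0.862
- half-width = 1.96 × √(0.9 × 0.1/37 + 1.96²/(4 × 37²)) / (1 + 1.96²/37) = 0.099
- limits 0.763 and 0.962, width 0.199

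This depends only on the proportion scoring 3 to 5, so relabelling the ends does not change it.

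**3. The pass mark.** 0.90 × 37 = 33.3, so 34 favourable answers are needed (33/37 = 89.2%, 34/37 = 91.9%) and at most 3 unfavourable answers are allowed. At the Scenario 2 look, 0.90 × 50 = 45.

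**4. Effect of misreading.** The documents give no misreading rate, so the shares are assumptions shown over a range. Exams are treated as independent.

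- Type (b): with true same-or-better rate p and a share m of truly harder exams marked *Very Easy*, the recorded rate is p′ = p + m(1 − p).
- Type (a): with a share k of favourable exams marked *Very Hard*, p′ = p(1 − k).
- First look: P(X ≥ 34), with X ~ Binomial(37, p′).
- With the second look, on this item alone: P(X ≥ 34) + Σ P(X = x) × P(Y ≥ 45 − x), summed over x = 19 to 33, with Y ~ Binomial(13, p′). The sum starts at 19 because 18/37 = 48.6% falls below the 50% floor of Scenario 2.

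| True rate | Assumed misreading | p′ | Met at 37 | Met at 37 or 50 |
|---|---|---|---|---|
| 80% | none | 0.80 | 4.5% | 7% |
| 80% | m = 10% | 0.82 | 8.0% | 12% |
| 80% | m = 25% | 0.85 | 17.4% | 26% |
| 80% | m = 50% | 0.90 | 48.6% | 65% |
| 95% | none | 0.95 | 88.8% | 97% |
| 95% | k = 1% | 0.9405 | 82.4% | 93% |
| 95% | k = 3% | 0.9215 | 67.0% | 83% |
| 95% | k = 5% | 0.9025 | 50.7% | 67% |

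The second look softens the loss in direction (a) and enlarges the gain in direction (b).

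**The case against.** The strongest reply is that the layout already signals the intended reading. The question opens by naming the first scope as reference, the midpoint is *Same*, and *Harder* and *Easier* flank it. Case (b) needs a surgeon who found the FNS harder to pass over the option that says so and tick the opposite end. The raters are faculty surgeons trained on the study and the device before recruitment. This stands as a reason to expect few misreadings. It does not exclude them, since no described training or instruction covers how to read the end labels.

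The same material answers four stronger readings that a reader might infer:

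- *That section 12.3 defines the score only in absolute terms.* It does not. It names the outcome a comparison, and Scenario 1 scores the second scope against the first.
- *That a 1 or a 5 cannot be interpreted afterwards.* The survey asks for an explanation of every answer on the hard side, which also shows that it treats 1 and 2 as one unfavourable group. A 1 given because both scopes were hard may therefore come with its reason. The gap remains for a 5, which prompts nothing. The satisfaction and structures-seen items for each scope and the technical-issues list for the FNS are partial cross-checks, not ease ratings.
- *That this score alone decides success.* It is one of three joint conditions: it can block success but not grant it.
- *That missing 34 of 37 fails an equal device.* Scenario 2 can continue to 50 subjects and apply the rule again, and the consequence of missing it then is fine-tuning the prototype.

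**Conclusion.** The point holds as a defect of wording in the primary instrument. The item mixes two frames of reference, the absolute labels sit on opposite sides of the success cut, and nothing in the documents fixes their meaning. The documents do not show that the score fails to measure FNS against SOC; they show only that it need not do so for every rater.

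The size depends wholly on the assumed misreading shares. Small shares of truly harder exams marked *Very Easy* matter little: 10% moves 4.5% to 8.0% at the first look. The larger effects need shares up to 50%. In the other direction the rule is more sensitive, because only 3 unfavourable answers are allowed: a 1% share already moves 88.8% to 82.4%. These probabilities concern the ease criterion alone, not overall success.

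Severity is moderate to minor. The correction is worth making because it is simple and because the reference behind a recorded 5 cannot be recovered once the data are in.

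**What to change.** In section 3, section 3.1 and the clinician survey, label the item on one relative scale: 1 = much harder than the first scope, 2 = harder, 3 = same, 4 = easier, 5 = much easier. Keep the 3-to-5 success cut.

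In section 12.3, replace the two end labels, and the word *excellent* where it refers to this outcome, with the matching terms. Change the survey's free-text prompt so that it refers to answers of harder or much harder.

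The cost is two labels and one prompt on the REDCap form, plus matching protocol wording, submitted for the IRB and NIDCR approval that section 15.2 requires for amendments. No extra data, subjects or clinic time are needed, and n = 37 and its interval stay as they are. The change should be in place before data collection begins.
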